### **2.8.1 Adverse events (AEs)**

AEs will be graded according to the CTCAE, Version 4.0. Adverse events will be coded to the preferred term (PT) level using the Medical Dictionary for Regulatory Affairs (MedDRA dictionary). The latest available MedDRA version at the time of the analyses will be used. The MedDRA version used for reporting will be specified in the CSR and as a footnote in the applicable tables/listings.

AE summaries will include all AEs occurring during on treatment period. All AEs collected in the AE eCRF page will be listed along with information collected on those AEs (e.g. AE relationship to study drug, AE outcome, etc.) AEs with start date outside of on-treatment period will be flagged in the listings.

AEs will be summarized by number and percentage of patients having at least one AE, having at least one AE in each primary system organ class (SOC) and for each preferred term (PT) using MedDRA coding. A patient with multiple occurrences of an AE will be counted only once in the respective AE category. A patient with multiple CTCAE grades for the same preferred term will be summarized under the maximum CTCAE grade recorded for the event. AE with missing CTCAE grade will be included in the 'All grades' column of the summary tables.

In AE summaries, the primary system organ class will be presented alphabetically and the preferred terms will be sorted within primary SOC in descending frequency. The sort order for the preferred term will be based on their frequency.

The following adverse event summaries will be produced by dose for Part A and Part C dose exploration, by disease cohorts for Part B, by tumor-specific cohorts for Part D, by age group (< 2 years, 2 to < 6, 6 to 12, and 12 to 18 years) for monotherapy (Part A and Part B combined) and combination therapy (Part C and Part D combined) ;

- overview of adverse events
- Overview of deaths and SAEs,
- AEs by SOC, PT and severity (post-text)
- AEs by SOC and severity (in-text)
- AEs by PT and severity (in-text)
- AEs suspected to be related by SOC, PT and severity (post-text),
- AEs suspected to be related by PT and severity (in-text),
- SAEs by SOC, PT and severity (post-text)
- SAEs by PT and severity (in-text)
- AEs leading to study treatment discontinuation by SOC, PT and severity (post-text)
- AEs leading to study drug discontinuation by PT and severity (in-text),
- AEs leading to dose reductions, leading to dose interruptions, and leading to fatal outcome (post-text).

- AESIs (in-text)

A summary of serious and non-serious adverse events with number of occurrences will be produced as per EudraCT requirements.

For the legal requirements of ClinicalTrials.gov and EudraCT, two required tables for on-treatment adverse event which are not SAE's with an incidence greater than and equal to 5% and on on-treatment SAE's and SAE's suspected to be related to study treatment will be provided by system organ class and preferred term on the safety set population.

If for a same patient, several consecutive AEs (irrespective of study treatment causality, seriousness and severity) occurred with the same SOC and PT:

- a single occurrence will be counted if there is  $\leq 1$  day gap between the end date of the preceding AE and the start date of the consecutive AE
- more than one occurrence will be counted if there is  $> 1$  day gap between the end date of the preceding AE and the start date of the consecutive AE

For occurrence, the presence of at least one SAE / SAE suspected to be related to study treatment / non SAE has to be checked in a block e.g., among AE's in a  $\leq 1$  day gap block, if at least one SAE is occurring, then one occurrence is calculated for that SAE.

The number of deaths resulting from SAEs suspected to be related to study treatment and SAEs irrespective of study treatment relationship will be provided by SOC and PT.

### **Dose Limiting Toxicity**

An AE will be considered a DLT if it is considered by the investigator to be at least possibly related to study treatment, meets any of the criteria listed in Section 3.2.3.1 or Section 3.2.3.2 of protocol and occurred during the first 28 days of treatment in the dose determining portion of the study (Part A and 3+3 design portions of Part A extension, Part C and Part C extension).

DLTs will be listed and summarized for age and the dose determining portion of Part A and Part C. Only the first cycle (28 days) of treatment will be considered when summarizing data regarding the dose limiting toxicities. The table will display the number of DLT's at each dose level. AE summary of DLTs will also be presented.

Note that isolated clinical laboratory value(s) considered **not** clinically significant by the investigators are not AEs and therefore, would not be DLTs.

#### **2.8.1.1 Adverse events of special interest / grouping of AEs**

##### **Data analysis of AESIs**

An adverse event of special interest (AESI) is a grouping of adverse events that are of scientific and medical concern specific to compound, dabrafenib and trametinib. These groupings are defined using MedDRA terms, SMQs (standardized MedDRA queries), HGLTs (high level group terms), HLT (high level terms) and PTs (preferred terms). Customized SMQs (Novartis

MedDRA queries, NMQ) may also be used. A NMQ is a customized group of search terms which defines a medical concept for which there is no official SMQ available or the available SMQ does not completely fit the need. It may include a combination of single terms and/or an existing SMQ, narrow or broad. For each specified AESI, number and percentage of patients with at least one event of the AESI occurring during on treatment period will be summarized. The events considered as AESI's will be based off of the latest CRS.

Summaries of these AESIs will be provided by trametinib and dabrafenib, by dose and study part, (specifying grade, SAE, relationship, leading to treatment discontinuation, leading to dose adjustment/interruption, hospitalization, death etc.). If sufficient number of events occurred, analysis of time to first occurrence will be applied.

A listing of all grouping levels down to the MedDRA preferred terms used to define each AESI will be generated.

### **2.8.2 Deaths**

In the event that a patient has withdrawn consent, no data after the withdrawal of consent date from this patient including death is supposed to appear in the database, which should be part of the data cleaning process.

Separate summaries for on-treatment and all deaths will be produced by study part, system organ class and preferred term.

All deaths will be listed, post treatment deaths will be flagged. A separate listing of deaths prior to starting treatment will be provided for all screened subjects.

### **2.8.3 Laboratory data**

On analyzing laboratory, data from all sources (central and local laboratories) will be combined. The summaries will include all assessments available for the lab parameter collected no later than 30 days after the last study treatment administration date (see Section 2.1.1).

The following summaries will be produced for hematology and biochemistry laboratory data (by laboratory parameter and study part):

- Worst post-baseline CTCAE grade (regardless of baseline status). Each patient will be counted only for the worst grade observed post-baseline.
- Shift tables using CTCAE grades to compare baseline to the worst post-baseline value
- For laboratory tests where CTCAE grades are not defined, shift tables using the low/normal/high classification to compare baseline to the worst post-baseline value.
- Trends of lab parameter values over time (baseline and selected on-treatment time points) should be displayed via boxplots based on time windows and corresponding tables displaying the statistics used for the box plots by the selected time points.

The following listings will be produced for laboratory data:

- Listings of all laboratory data, with CTC grades and classification relative to the laboratory normal range. Lab data collected during the post-treatment period will be flagged.
- Listing of all CTC grade 3 or 4 laboratory toxicities

For laboratory tests (e.g. potassium, sodium, calcium, glucose, magnesium, hemoglobin and lymphocytes) that are graded for both low and high values, summaries will be done separately and labeled by direction, e.g. sodium will be summarized as hyponatremia and hypernatremia.

Unless otherwise specified, the denominator in percentage calculation at each scheduled visit will be based on the number of patients with non-missing value at each particular visit.

### **Liver function parameters**

Liver function parameters of interest are total bilirubin (TBL), ALT, AST and alkaline phosphatase (ALP). The number (%) of patients with worst post-baseline values as per Novartis Liver Toxicity guidelines will be summarized:

The following summaries will be produced:

- AST or ALT > 3 x Baseline
- ALT or AST > 3xULN
- ALT or AST > 5xULN
- ALT or AST > 8xULN
- ALT or AST > 10xULN
- ALT or AST > 20xULN
- TBL > 2 x Baseline
- TBL > 2xULN
- TBL > 3xULN
- ALT or AST > 3xULN & TBL > 2xULN
- ALT or AST > 3xULN & TBL > 2xULN & ALP < 2xULN
- [AST or ALT > 3 x Baseline] & [TBL > 2 x Baseline AND TBL > 2.0 x ULN]
- [AST or ALT > 8.0 x ULN] & [TBL > 2 x Baseline AND TBL > 2.0 x ULN]
- Lower ([AST or ALT > 3 x Baseline] OR [AST or ALT > 8.0 x ULN]) & [TBL > 2 x Baseline AND TBL > 2.0 x ULN]

A clinically significant liver safety signal corresponding to Hy's Law events are defined as a patient with abnormal ALT or AST baseline value and combined elevations post baseline (based on the peak values at any post-baseline time for a patient). [AST or ALT > 3 x Baseline] OR [AST or ALT > 8.0 x ULN], whichever is lower and combined with [TBL > 2 x Baseline AND TBL > 2.0 x ULN]

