**Part C** will be a limited dose escalation part of the study evaluating the combination of trametinib with dabrafenib in children and adolescents with recurrent, refractory or unresectable BRAF V600 mutated tumors. This part of the study will establish recommended Phase 2 doses (RP2D) of dabrafenib and trametinib when given in combination in children and adolescents. This part of the study will enroll approximately 18 subjects (including up to 6 adolescent subjects with BRAF V600 mutant metastatic melanoma) and will not open to accrual until the dose of dabrafenib in children is established in study BRF116013, the dose of trametinib is established in Part A and review of the available safety and PK data of trametinib and dabrafenib monotherapy in children is completed. Amendment 3 provides the updated safety data and dabrafenib dosing in children. Parts B and C may be open to accrual simultaneously. Patients who have had prior dabrafenib therapy may enroll in part C if they have had prior benefit to dabrafenib monotherapy, as determined by the investigator.

**Part C extension** will be an age-specific dose exploration in 6 subjects aged 12 months to < 6 years old. If the trametinib dose of 0.032 mg/kg/day is tolerated in Part A extension, a combination of trametinib 0.032mg/kg/day and the full dabrafenib pediatric RP2D will be tested in this cohort. The goal of this additional dose exploration is to establish the safety, tolerability, PK and RP2D of the trametinib and dabrafenib combination in this younger age cohort

**Part D** will be a tumor cohort expansion part of the study to further evaluate the safety, tolerability, and preliminary clinical activity of the combination of trametinib and dabrafenib in tumor-specific pediatric populations listed below.

- D1: BRAF V600-mutant, relapsed or refractory low grade glioma (LGG)
- D2: BRAF V600-mutant, relapsed or refractory Langerhans cell histiocytosis (LCH)

Disease cohorts are selected based on current data of proto-oncogene RAS (Ras)/ mitogen-activated protein kinase (MAPK) activation in childhood solid tumors. Pediatric subjects 12 months to < 18 years of age are to be enrolled. Approximately 20 subjects with LGG and 10 subjects with LCH will be enrolled.

Subjects may not enroll in more than one part of the study. Subjects will receive study treatment until disease progression, death or unacceptable toxicity.

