### **Windows for multiple assessments**

In order to summarize (vital sign, performance status, etc.) data collected over time (including unscheduled visits), the assessments will be time slotted. The following general rule will be applied in creating the assessment windows: If more than one assessment is done within the same time window, the assessment performed closest to the target date will be used. If 2 assessments within a time window are equidistant from the target date, then the worse of 2 assessments (i.e. farthest outside the normal range) will be used. If multiple assessment are on the same date then the worst case will be used. Data from all assessments (scheduled and unscheduled), including multiple assessments, will be listed.

For all analyses regarding abnormal assessments or analyses based on worst or best post-baseline value (laboratory, ECGs, vital signs, Karnofsky/Lansky performance status, ECHO etc.), all post-baseline values will be included (scheduled, unscheduled, repeat).

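### The liver row requiring ALP below 2 x ULN is counted on worst post-baseline values with no timing rule for ALP, so an ALP rise at another time can misclassify a concurrent ALT/bilirubin case

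*SAP*

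**What the plan says.** All the liver rows in SAP Section 2.8.3, single and combined, stand under one lead-in: "The number (%) of patients with worst post-baseline values as per Novartis Liver Toxicity guidelines will be summarized". Two of the combined rows are adjacent. One is "ALT or AST > 3xULN & TBL > 2xULN"; the next adds the ALP condition, "ALT or AST > 3xULN & TBL > 2xULN & ALP < 2xULN".

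After the rows, the SAP defines Hy's Law events for patients whose baseline ALT or AST is abnormal. The combined elevations there are "based on the peak values at any post-baseline time for a patient". That definition has no ALP term.

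Two other places decide which values enter. Under Windows for multiple assessments (Section 2.1.1), analyses of worst or best values take everything: "all post-baseline values will be included (scheduled, unscheduled, repeat"). Section 2.8.3 sets the outer limit, using assessments "collected no later than 30 days after the last study treatment administration date". Section 1.1 leaves treatment duration open: "Subjects will receive study treatment until disease progression, death or unacceptable toxicity".

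The SAP nowhere requires the ALT/AST and bilirubin elevations to be concurrent or within a stated number of days, and it does not say which ALP value is compared with 2 x ULN.

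**The concern.** The ALP condition separates hepatocellular injury from cholestasis. That distinction concerns the time at which ALT/AST and bilirubin rise together. Tested on the patient's worst ALP over the whole observation period, it asks a different question: whether ALP ever reached 2 x ULN.

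Worst-value rules normally make a safety display more sensitive. For ALT/AST and bilirubin, where a high value qualifies the patient, they do. For ALP, where a high value disqualifies the patient, the same rule removes cases. The longer a patient is observed, the more chances there are for an ALP rise at another time to do so.

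The Hy's Law sentence raises a second, milder issue. It pairs peaks from any time and calls the result a clinically significant signal, so a reader may take each count to be a concurrent event. Elsewhere the SAP does fix timing when analytes are combined: corrected calcium (Section 5.3) takes albumin from the same assessment.

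**Working it through.** The SAP gives no count or rate for these rows, so there is no figure to reproduce. The check applies the stated rule to invented patients and compares it with a same-visit rule.

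**Rules compared**
- Worst-value rule: max(ALT) > 3 and max(TBL) > 2 and max(ALP) < 2, each maximum over all post-baseline visits.
- Same-visit rule: at least one visit with ALT > 3 and TBL > 2 and ALP < 2.

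**Illustrative records** (assumed values, multiples of ULN, given as ALT / TBL / ALP)
- A: 4 / 2.5 / 1.2, then 1 / 1 / 1.0, then 1 / 1 / 2.3
- B: 4 / 0.8 / 1.0, then 1 / 0.9 / 1.0, then 1 / 2.4 / 1.1
- C: 4 / 2.5 / 1.2, then 1 / 1 / 1

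| Patient | ALP row, worst-value | ALP row, same-visit | Row without ALP, worst-value | Row without ALP, same-visit |
|---|---|---|---|---|
| A | no (max ALP 2.3) | yes | yes | yes |
| B | yes | no | yes | no |
| C | yes | yes | yes | yes |

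Patient A is the main point: ALP was 1.2 when ALT and bilirubin were both raised, yet a later 2.3 takes the patient out of the ALP row. A remains in the row without ALP. Patient B shows the pairing effect: two elevations that never coincided count as one combination.

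**Readings of the ALP condition for patient A** (ALP 1.2, 1.0, 2.3)
- Highest value: 2.3, fails.
- Any value below 2: passes. But almost every patient has such a value, so the condition would filter very little.
- Value at the qualifying elevation: 1.2, passes.

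The worst-value lead-in points to the first reading, but it is not written out.

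**Hy's Law definition for patient B.** Baseline ALT must be abnormal, so above 1 x ULN. The peak of 4 exceeds 3 x baseline if baseline is below 4/3 = 1.33 x ULN. The bilirubin peak of 2.4 exceeds 2 x ULN, and exceeds 2 x baseline if baseline is below 2.4/2 = 1.2 x ULN. With baselines in those ranges, B meets the definition without any concurrent elevation.

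**Size.** Planned cohorts are 10 (each Part B cohort, and LCH in Part D) and about 20 (LGG in Part D). One misclassified patient moves a row by 100/10 = 10 or 100/20 = 5 percentage points. The following figures are assumptions only:
- If 5% to 20% of true cases have an unrelated ALP of 2 x ULN or more at some other time, that same share leaves the ALP row.
- If ALT peaks above 3 x ULN in 15% of patients and TBL above 2 x ULN in 5%, independently, both peaks occur in 0.15 x 0.05 = 0.75%. This is an upper bound on non-concurrent pairs, since some pairs will coincide. It amounts to 10 x 0.0075 = 0.075 expected patients in a cohort of 10 and 20 x 0.0075 = 0.15 in a cohort of 20.

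**The case against.** Pairing ALT/AST and bilirubin peaks from any time is an openly stated choice. It errs toward over-detection, which is defensible for a descriptive display in a study that tests no hypotheses. This stands. A reader might infer that the pairing is an error in itself; the documents do not support that. What remains is the label.

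The any-time wording sits only in the Hy's Law sentence, which covers patients with abnormal baseline ALT or AST. This also stands: that sentence cannot be read as governing the ALP row. The row reaches the same result through the worst-value lead-in.

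The lead-in refers to the sponsor's liver toxicity guideline, which may fix the ALP timing. It is not shown and cannot be checked. The SAP text alone leaves the timing to the programmer.

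A reader might also infer that true cases disappear from the report. They do not. The patient in question still counts in the row directly above, and Section 2.8.3 provides listings of all laboratory data, from which timing can be checked patient by patient.

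Finally, the assumed rates imply few affected patients in cohorts this small, and the 10-point and 5-point shifts would apply to any row of any table. That limits the importance of the point. It does not answer the ALP problem, because the sensitive-screen argument does not cover a condition that excludes patients.

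**Conclusion.** The point holds in a limited form. On the natural reading that worst ALP means highest ALP, the row with ALP below 2 x ULN drops patients who had concurrent ALT/AST and bilirubin elevations without raised ALP, if ALP reached 2 x ULN at any other post-baseline time up to 30 days after last dose. This is misclassification between neighbouring rows of a summary table, not loss of data. The Hy's Law count is usable as a screen, but the SAP does not label it as one, and it can include elevations that never coincided.

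No misclassification rate can be derived from the SAP. The conclusion rests on the wording and on the reading of worst ALP just stated. Lengthy treatment gives the problem more opportunity to arise, but only for patients still on drug or within 30 days of their last dose.

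**What to change.** Three changes to Section 2.8.3, made before database lock:

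1. Evaluate the ALP condition at the qualifying ALT/AST and bilirubin elevation: in the same sample or, when samples differ, with the ALP value nearest the ALT/AST elevation. Do not use the patient's worst ALP.
2. Keep the any-time combined rows and the Hy's Law count, clearly labelled as a screen that does not require the elevations to be concurrent.
3. Add a count of patients whose ALT/AST and bilirubin elevations occur in the same sample or within a window. The SAP gives no window length; the sponsor should fix one before lock.

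The data are already collected. The cost is a few sentences and one merge of laboratory records by sample or date. A few cases will have tests drawn on different days; the window and the retained screening rows cover them.

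### The SAP's Hy's Law definition requires an abnormal baseline ALT or AST and has no branch for normal baselines, so the label can miss cases that the liver table still shows

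*SAP*

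**What the plan says.** Under Liver function parameters in SAP Section 2.8.3, the general instruction is: "The number (%) of patients with worst post-baseline values as per Novartis Liver Toxicity guidelines will be summarized". A list of rows follows. The rows that combine transaminases and bilirubin are of two kinds:

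- **ULN-based:** ALT or AST above 3xULN with TBL above 2xULN, first without an ALP condition and then as "ALT or AST > 3xULN & TBL > 2xULN & ALP < 2xULN".
- **Baseline-relative:** a transaminase condition (3 x baseline, 8 x ULN, or the lower of the two) joined to "TBL > 2 x Baseline AND TBL > 2.0 x ULN".

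None of these rows carries a condition on baseline ALT or AST status, and none is called Hy's Law.

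The closing sentence then defines the liver signal that corresponds to Hy's Law. These "events are defined as a patient with abnormal ALT or AST baseline value and combined elevations post baseline", with the thresholds "AST or ALT > 3 x Baseline] OR [AST or ALT > 8.0 x ULN], whichever is lower and combined with" the same bilirubin condition as above. No other part of the SAP defines the term.

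**The concern.** The definition joins an abnormal baseline ALT or AST to the post-baseline elevations by the word and, so it is a requirement. Nothing is said about patients who start with normal ALT and AST. A programmer or report author who applies the sentence as written would attach the Hy's Law label only to patients with an abnormal baseline.

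Changes in laboratory values are part of the primary endpoint in Parts A to D (SAP Section 2.5.1). A statement that no Hy's Law event occurred could then stand beside a non-zero count in the ULN-based combined row, and the SAP has no rule to reconcile them. The ULN row is not split by baseline status. The shift tables show baseline status one laboratory parameter at a time. The missing count therefore cannot be read from the planned summary tables and would have to be assembled from the listings.

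**Working it through.** No sample size, power or confidence interval figure is involved, so there is no stated number to reproduce. The check is to write the rules out and apply them to example patients.

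**Inputs.** The thresholds come from SAP Section 2.8.3. The patient values are assumptions for illustration, in multiples of ULN, with baseline bilirubin 0.5 and ALP 1 throughout. Abnormal baseline is taken as above ULN. Let b be baseline ALT, t baseline bilirubin, and ALT and TBL the post-baseline peaks.

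**Rules.**

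- Hy's Law as defined (H): b > 1, and ALT > min(3b, 8), and TBL > 2t, and TBL > 2.
- Last combined row, which begins with the word Lower (L): as H, without b > 1.
- ULN row with ALP (U): ALT > 3, and TBL > 2, and ALP < 2.

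Exceeding either of two thresholds is the same as exceeding the smaller one. The either/or wording and the whichever-is-lower wording therefore give one rule, min(3b, 8).

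**Results.** With t = 0.5, 2t = 1, so the bilirubin condition reduces to TBL > 2 in every row.

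| b | Peak ALT | Peak TBL | min(3b, 8) | H | L | U |
|---|---|---|---|---|---|---|
| 0.5 | 10 | 4 | 1.5 | no | yes | yes |
| 0.9 | 25 | 6 | 2.7 | no | yes | yes |
| 1.0 | 10 | 4 | 3.0 | no | yes | yes |
| 1.01 | 10 | 4 | 3.03 | yes | yes | yes |
| 1.5 | 5 | 3 | 4.5 | yes | yes | yes |
| 0.5 | 1.6 | 2.1 | 1.5 | no | yes | no |

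**Reading the table.**

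1. The third and fourth patients have identical post-baseline values. A baseline difference of 0.01xULN decides the label.
2. The first three patients have marked combined elevations and normal baselines. H excludes them; L and U count them.
3. The two transaminase thresholds cross where 3b = 8, at b = 8/3 = 2.67xULN. The cap at 8xULN matters only above that baseline, so the formula was evidently built for raised baselines. This is consistent with the normal-baseline half having been left out.
4. The last patient shows why deleting the word abnormal is not a repair. At b = 0.5 the threshold falls to 3 x 0.5 = 1.5xULN, so a peak ALT of 1.6xULN with TBL 2.1xULN would be labelled Hy's Law although it does not meet the ULN row.

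**The case against.** The strongest answer is that nothing is lost from the planned outputs. The ULN-based combined rows cover all patients. The row beginning with the word Lower is the definition's own formula without the baseline condition, and it also counts normal-baseline patients whose bilirubin exceeds twice baseline. The same section plans worst post-baseline grades whatever the baseline, shift tables, a full laboratory listing and a listing of grade 3 or 4 values. The SAP orders no separate Hy's Law table, and all analyses are descriptive (Section 2.5.2). The liver summaries also refer to a sponsor guideline that was not available for this review, and neither was the protocol. A normal-baseline branch may exist in one of them.

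Most of this stands. A reader might infer that liver injury in children with normal baseline tests would go unreported, or that a large, quantifiable part of the trial is shut out of the liver analysis. The document supports neither. Such patients stay visible in several rows, and the SAP gives no share of abnormal baselines. Even a known share would say who falls outside the label, not how many events are missed.

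The objection does not remove the defect. The sentence fixes what counts as the Hy's Law signal, and as written it misclassifies. The guideline is cited for the summary rows; the definition itself points to no other branch.

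**Conclusion.** The point holds as a defect in the labelled definition. Every patient with normal baseline ALT and AST is outside the Hy's Law label, however large the later combined elevation. This follows from the wording alone and does not depend on the example values. It is not a loss of data: the same patients appear in the unconditional combined rows whose thresholds they meet, in the shift tables and in the listings. The number of patients affected cannot be derived from the SAP.

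The conclusion assumes that the sentence is applied literally, that abnormal means above ULN, and that no normal-baseline branch is set in the protocol or the sponsor guideline. If one is set there, the SAP should state it or refer to it. The most likely explanation is a drafting omission. It should be corrected before database lock.

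**What to change.** Extend the definition in SAP Section 2.8.3:

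- **ALT and AST both normal at baseline:** name the existing row "ALT or AST > 3xULN & TBL > 2xULN & ALP < 2xULN" as the reporting criterion for Hy's Law.
- **ALT or AST abnormal at baseline:** keep the present wording.
- **Reporting:** give the Hy's Law count as the total of the two, with the split by baseline status shown. A footnote should say that the ALP condition applies to the normal-baseline branch only.
- **Missing baseline ALT or AST:** state separately how these patients are classed. Section 2.1.1 says only that their baseline result is missing.

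This concerns classification for reporting only. The cost is a sentence or two of SAP text and one extra table split, from data already planned for analysis. The reported Hy's Law count may be higher than under the present wording.
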